### 9.2.5 Serious Adverse Event (SAE)

A serious adverse event based on ICH and EU Guidelines on Pharmacovigilance for Medicinal Products for Human Use is any untoward medical occurrence that at any dose:

- Results in **death**.
- Is a **life-threatening** adverse experience. The term life-threatening in the definition of serious refers to an adverse event in which the subject was at risk of death at the time of the event. It

does not refer to an adverse event which hypothetically might have caused death if it were more severe.

- Requires **inpatient hospitalization or prolongation of existing hospitalization for AEs related to study drug and not for the scheduled radical prostatectomy**. Any adverse event leading to hospitalization or prolongation of hospitalization will be considered as Serious, UNLESS at least one of the following expectations is met:
  - The admission results in a hospital stay of less than 24 hours OR
  - The admission is pre-planned (e.g., elective or scheduled surgery arranged prior to the start of the study) OR
  - The admission is not associated with an adverse event (e.g., social hospitalization for purposes of respite care.
  - However it should be noted that invasive treatment during any hospitalization may fulfill the criteria of “medically important” and as such may be reportable as a serious adverse event dependent on clinical judgment. In addition where local regulatory authorities specifically require a more stringent definition, the local regulation takes precedent.
- Results in **persistent or significant disability/incapacity**. The definition of disability is a substantial disruption of a person’s ability to conduct normal life’s functions.
- Is a **congenital anomaly/birth defect**.
- Is a suspected transmission of any infectious agent via a medicinal product.
- Is an **important medical event**. Important medical events that may not result death, be life-threatening, or require hospitalization may be considered a serious adverse experience when, based upon appropriate medical judgment, they may jeopardize the subject and may require medical or surgical intervention to prevent one of the outcomes listed in this definition. Examples of such medical events include allergic bronchospasm requiring intensive treatment in an emergency room or at home, blood disease or disorders, or convulsions that do not result in inpatient hospitalization, or the development of drug dependency or drug abuse. The development of a new cancer is always considered an important medical event.

**NOTE: DEATH FOR ANY REASON SHOULD BE REPORTED AS A SERIOUS ADVERSE EVENT WITHIN 30-DAYS OF THE LAST DOSE OF APALUTAMIDE AS STATED IN SECTION 9.2.5.2.**

SAE reports and any other relevant safety information are to be emailed to [name] at [[contact]](mailto:[contact]) and to the Cleveland Clinic SAE inbox at [[contact]](mailto:[contact]).

SAE reports and any other relevant safety information are also to be sent to the COMPANY (Janssen Research & Development, LLC) within 24 hours via secure email at [[contact]](mailto:[contact]) as described in sections 9.7.1 and 9.9.

#### 9.2.5.1 Hospitalization

For reports of hospitalization, it is the sign, symptom or diagnosis which led to the hospitalization that is the serious event for which details must be provided.

Any event requiring hospitalization or prolongation of hospitalization that occurs during the study must be reported as a serious adverse event, except hospitalizations for the following:

- Hospitalizations not intended to treat an acute illness or adverse event (e.g., social reasons such as pending placement in long-term care facility)
- Surgery or procedure planned before entry into the study. [Note: Hospitalizations that were planned before the start of data collection and where the underlying condition for which the hospitalization was planned has not worsened will not be considered serious adverse events. Any adverse event that results in a prolongation of the originally planned hospitalization is to be reported as a new serious adverse event.]

#### 9.2.5.2 Life-Threatening Conditions

The cause of death of a subject in a study within 30-days of the last dose of Apalutamide whether or not the event is expected or associated with the study drug, is considered a serious adverse event.

Disease progression should not be recorded as an adverse event or serious adverse event term; instead, signs and symptoms of clinical sequelae resulting from disease progression/lack of efficacy will be reported if they fulfill the serious adverse event definition.

### 9.3 Unlisted (Unexpected) Adverse Event/Reference Safety Information

An adverse event is considered unlisted if the nature or severity is not consistent with the applicable product reference safety information. For a medicinal product(s) with a marketing authorization, the expectedness of an adverse event will be determined by whether or not it is listed in the applicable product information.

For Apalutamide, the expectedness of an adverse event will be determined by whether or not it is listed in the applicable product information.

For Apalutamide, the link to the package insert is:

<http://www.janssenlabels.com/package-insert/product-monograph/prescribing-information/ERLEADA-pi.pdf>

### 9.4 Special Reporting Situations

Safety events of interest for a Janssen medicinal product that require expediting reporting and/or safety evaluation include, but are not limited to:

- Drug exposure during pregnancy (maternal and paternal)

- Overdose of a Janssen medicinal product  
Exposure to a Janssen medicinal product from breastfeeding
- Suspected abuse/misuse of a Janssen medicinal product
- Inadvertent or accidental exposure to a Janssen medicinal product
- Medication error involving a Janssen medicinal product (with or without patient exposure to the Janssen medicinal product, e.g., name confusion)
- Suspected transmission of any infectious agent via administration of a medicinal product

These safety events may not meet the definition of an adverse event; however, from Janssen Scientific Affairs perspective, they are treated in the same manner as adverse events. Special situations should be recorded on the Adverse Event page of the CRF.

Any special situation that meets the criteria of a serious adverse event should be recorded on a Serious Adverse Event Report Form and be reported to Janssen Scientific Affairs **within 24 hours of becoming aware of the event.**

## 9.5 Pregnancy

Because the Janssen medicinal product may have an effect on sperm, pregnancies in partners of male subjects exposed to a Janssen medicinal product will be reported by the PRINCIPAL INVESTIGATOR **within 24 hours of their knowledge of the event** using the Serious Adverse Event Form. Depending on local legislation this may require prior consent of the partner.

Follow-up information regarding the outcome of the pregnancy and any postnatal sequelae in the infant will be required.

## 9.6 Maintenance of Safety Information

All safety data should be maintained in a clinical database in a retrievable format. The INSTITUTION and PRINCIPAL INVESTIGATOR shall provide all adverse events, both serious and non-serious, in report format. However, in certain circumstances more frequent provision of safety data may be necessary, e.g. to fulfill a regulatory request, and as such the data shall be made available within a reasonable timeframe at Janssen Scientific Affairs' request.

## 9.7 Procedures for Reporting Safety Data and Product Quality Complaints (PQCs) for Janssen Medicinal Products to the COMPANY

All adverse events and special situations whether serious or non-serious, related or not related, following exposure to a Janssen medicinal product are to be documented by the investigator and recorded in the CRF and in the subject's source records. Investigators must record in the CRF their opinion concerning the relationship of the adverse event to a Janssen medicinal product.

All (serious and non-serious) adverse events reported for a Janssen medicinal product should be followed up in accordance with clinical practice.

#### 9.7.1 SAEs and Special Reporting Situations

All serious adverse events that have not resolved by the end of the study, or that have not resolved upon discontinuation of the subject's participation in the study, must be followed until any of the following occurs:

- The event resolves
- The event stabilizes
- The event returns to baseline, if a baseline value/status is available
- The event can be attributed to agents other than the study drug or to factors unrelated to study conduct
- It becomes unlikely that any additional information can be obtained (subject or health care practitioner refusal to provide additional information, lost to follow-up after demonstration of due diligence with follow-up efforts)
  
- The INSTITUTION and the PRINCIPAL INVESTIGATOR will transmit all SAEs and special situations following exposure to a Janssen product under study in a form provided by the COMPANY **within 24-hours of becoming aware of the event(s).**
  
- All follow-up information for serious adverse events that are not resolved at the end of the study or by the time of patient withdrawal must be reported directly by the PRINCIPAL INVESTIGATOR, **within 24 hours becoming aware,** to the COMPANY using the COMPANY's Serious Adverse Event Report.
  
- All available clinical information relevant to the evaluation of a related SAE, serious ADR or special situation is required.
  
- The INSTITUTION and/or PRINCIPAL INVESTIGATOR are responsible for ensuring that these cases are complete and if not are promptly followed-up. A safety report is not considered complete until all clinical details needed to interpret the case are received. Reporting of follow-up information should follow the same timeline as initial reports.
  
- Copies of any and all relevant correspondences with regulatory authorities and ethics committees regarding any and all serious adverse events, irrespective of association with the Janssen Product under study, are to be provided to the COMPANY within **24 hours of such report or correspondence being sent to applicable health authorities.**

#### 9.7.2 Non-Serious AEs

All non-serious adverse events should be reported to COMPANY according to the timeframe

outlined in the Research Funding Agreement section entitled Reporting of Data.

**SAE Report Form** SAEs will be recorded on the FDA Form 3500A (MedWatch) but should only be reported as instructed below. The electronic FDA SAE reporting forms should not be used.

### 9.7.3 PQC Reporting

A PQC may have an impact on the safety and efficacy of the product. Timely, accurate, and complete reporting and analysis of PQC information from studies are crucial for the protection of patients, investigators, and the COMPANY, and are mandated by regulatory agencies worldwide. The COMPANY has established procedures in conformity with regulatory requirements worldwide to ensure appropriate reporting of PQC information. Lot and/or Batch #s shall be collected or any reports failure of expected pharmacological action (i.e., lack of effect). The product should be quarantined immediately and if possible, take a picture.

All initial PQCs involving a Janssen medicinal product under study must be reported to the COMPANY by the PRINCIPAL INVESTIGATOR within 24 hours after being made aware of the event.

If the defect for a Janssen medicinal product under study is combined with either a serious adverse event or non-serious adverse event, the PRINCIPAL INVESTIGATOR must report the PQC to the COMPANY according to the serious adverse event reporting timelines. A sample of the suspected product should be maintained for further investigation if requested by the COMPANY.

## 9.8 Reporting Procedures for Reporting Safety Data and Product Quality Complaints (PQCs) for Non-Janssen Medicinal Products

For SAEs, special reporting situations and PQCs following exposure to a non-Janssen medicinal product under study, the PRINCIPAL INVESTIGATOR should notify the appropriate regulatory/competent authority or the manufacturer of that medicinal product (in the absence of appropriate local legislation) as soon as possible.

## 9.9 Transmission Methods

The following methods are acceptable for transmission of safety information to the COMPANY:

- Electronically via Janssen SECURE Email service at [contact] (preferred)
- For business continuity purposes, if SECURE Email is non-functional:
  - Facsimile (fax) to [name], receipt of which is evidenced in a successful fax transmission report
- Telephone (if fax is non-functional).

Please use the contact information and process information provided by the COMPANY.

### 9.10 Reporting Procedures for Serious Adverse Events

For the purposes of safety reporting, all adverse events will be reported that occur after taking the first dose of Apalutamide through 30 days after the final dose of study drug. Adverse events, both serious and non-serious, and deaths that occur during this period will be recorded in the source documents. All SAEs should be monitored until they are resolved or are clearly determined to be due to a subject's stable or chronic condition or intercurrent illness (es). Related AEs will be followed until resolution to baseline or grade 1 or stabilization.

### 9.11 Institutional Review Board Reporting Requirements:

Investigative sites will report adverse events to their respective IRB according to the local IRB's policies and procedures in reporting adverse events.

### 9.12 SAEs and OnCore

- All SAEs will be entered into OnCore.
- A copy of the SAE form(s) submitted to the sponsor-investigator is also uploaded into OnCore

### 9.13 Data Safety and Toxicity Committee

It is the responsibility of each site PI to ensure that ALL SAEs occurring on this trial (internal or external) are reported to the Case Comprehensive Cancer Center's Data and Safety Toxicity Committee. This submission is simultaneous with their submission to Janssen Scientific Affairs, LLC and/or other regulatory bodies.

The sponsor-investigator is responsible for submitting an annual report to the DSTC as per CCCC Data and Safety Monitoring Plan.

### 9.14 Data and Safety Monitoring Plan (DSMP)

This protocol will adhere to the policies of the Case Comprehensive Cancer Center Data and Safety Monitoring Plan in accordance with NCI guidelines.

### 9.15 Criteria for Defining the Severity of an Adverse Event

9.15.1 Severity of adverse events will be graded according to the Cancer Therapy and Evaluation Program (CTCAE) Common Terminology Criteria for Adverse Events v. 4.0 available at <http://ctep.cancer.gov>. For terms not specified within NCI-CTCAE, the following guideline should be used to determine grade:

**Table 2. Criteria for Severity of Adverse Event Terms Not Specified Within NCICTCAE**

Toxicity Grade	Description
----------------	-------------

Grade 1	Mild; asymptomatic or mild symptoms, clinical or diagnostic observations only; intervention not indicated.
Grade 2	Moderate; minimal, local or noninvasive intervention indicated; limiting age appropriate instrumental activities of daily living.
Grade 3	Severe or medically significant but not immediately life-threatening; hospitalization or prolongation or hospitalization indicated; disabling; limiting self care activities of daily living
Grade 4	Life-threatening consequences; urgent intervention indicated.
Grade 5	Death related to AE.

### 9.16 End of Treatment

A patient may be discontinued from study treatment at any time if the patient, the Investigator and his (her) team, feels that it is not in the patient's best interest to continue on study. The following is a list of possible reasons for early discontinuation of study treatment:

- Disease progression
- Any episode of seizure
- Any other adverse event that cannot be adequately managed with dose modifications, including dose interruption for up to 7 days
- Protocol violation requiring discontinuation of study treatment
- Patient is not compliant with study procedures
- Lost to follow-up
- Patient withdrawal of consent
- Sponsor request for early termination of study

Patients will be followed for at least 28 +/-7 calendar days after the last dose of study drug. If a patient is withdrawn from treatment due to an adverse event, the patient will be followed until the adverse event has resolved or stabilized as per Section 7.6.

#### 9.16.1 Data to be collected for the end of treatment visit:

- Record any adverse events (optional if performed within 1 week)
- Record changes to concomitant medications (optional if performed within 1 week)
- Assess study drug compliance
- Perform abbreviated physical examination (optional if performed within 1 week)

- Perform and record vital signs and ECOG performance status (optional if performed within 1 week)
- Collect blood and urine for clinical laboratory assessments (optional if performed within 1 week)

#### 9.16.2 Safety Follow-Up (4-8 weeks following the Last Dose of Study Drug)

- Record any adverse events
- Record changes to concomitant medications

## 10 Tissue Studies

### 10.1 Tissue Procurement

Radical prostatectomy tissue will be processed in a standardized fashion according to institutional protocols established by the Specimen Core. Immediately after removal, prostatectomy specimens will be transferred into sterile ice-cold slurry of normal saline. Specimens will be accessioned and assigned a research number by the Tumor Procurement Service and tissue for study will be harvested according to standard protocols established and described in the Specimen Core and processed for pathological analysis as per established standards. Once harvested, the tissue to be used for this study will be snap frozen in liquid nitrogen and stored at -80 degrees until required for the planned analysis. All study related tissue (after official pathology review) will be stored within the GU core pathology department following standard institutional procedures and policies. Access to study tissue will be granted to appropriate personnel listed in the study protocol.

### 10.2 *HSD3B1* genotyping

#### 10.2.1 *HSD3B1* Genotyping By Sequencing

Genomic DNA will be prepared from peripheral blood using DNeasy Blood and Tissue Kit (QIAGEN, Germantown, MD). *HSD3B1* genotyping will be determined through a melting curve analysis on an ABI 7500 Real Time PCR System (Applied Biosystem, Carlsbad, CA). To determine genotype of *HSD3B1*, primer set ( Forward: 5'-GTCAAATAGCGTATTCACCTTCTCTTAT-3' and Reverse 5'-GAGGGTGGAGCTTGATGACATCT-3') and probe (GGAGA+ACCTGAAGTCCAAGACTCAGTGATTAAGG) will be used. The assay will consist of an initial denaturing set at 95°C for 2m, followed by amplification for 60 cycles of 95°C for 30s, 66°C for 30s and 75°C for 30s. A melting curve will follow amplification (95°C for 30s, 25°C for 60s, 50°C for 15s and final ramp rate (0.3%-1%) to 95°C for 15s. Each reaction will be done with 40 ng DNA, 50nM forward primer, 500nM reverse primer, and Light scanner HRM LC green Master Mix (Biofire Diagnostics, Salt Lake City, Utah).

#### 10.2.2 *HSD3B1* Genotyping by Melting Curve Assay

Genomic DNA will be prepared from peripheral blood using DNeasy Blood and Tissue Kit (QIAGEN, Germantown, MD). PCR products of the promoter region, all exons, exon-intron junctions and the

30-UTR will be sequenced to identify mutations in *HSD3B1*. To sequence the 30 flanking region of *HSD3B1*, primer set (Forward: 50-ATGTGGAGGGAGGTGTGAGT-30 and Reverse: 50-ACGGAGATGGGTCTCTTCCA-30 ) will be used with an annealing temperature of 62\_C. Genotyping PCR reaction (50 ml) will be done with 30-100 ng genomic DNA, 1 x PCR buffer with 0.2 mM dNTP, 0.2 mM of each primer, and 0.5 ml Phusion High-Fidelity DNA Polymerase (New England BioLabs Inc, Ipswich, MA). 1 mL purple top tube will be used for genotyping purposes at indicated time points.

### 10.3 Immunohistochemical Staining Of Cellular And Molecular Markers In Prostate Tumor Tissue

IHC for PSA will be performed as routinely done by [name] in the pathology department at the Cleveland Clinic.

### 10.4 Steroid Extraction and Measurements

Prostate tissue (20mg) will be homogenized using a Minilyse bead homogenizer (Bergin Corp, Rockville, MD). Steroids and internal standard will be extracted using methyl tart Butyl-ether (Sigma-Aldrich, St. Louis, MO). Steroids will be derivative using a Girard T reagent (Sigma-Aldrich, St. Louis, MO) as previously described (22). Steroid concentrations will be assessed through stable isotope ratios and quantitated using developed methodology on a liquid chromatography mass spectrometer. 1 10mL red top tube will be used for serum steroid studies at indicated time points.

### 10.5 mRNA Expression

Prostate tissue (<20 mg) will be homogenized and RNA will be extracted using a Gene lute Mammalian Total RNA Miniprep Kit ( Sigma Aldrich, St. Louis, MO). Extracted RNA will be synthesized into cDNA using an iScript cDNA Synthesis Kit (Bio-Rad, Hercules, CA). Expression for PSA, TMPRSS2, FKBP5, EZH2, H3K27, and UBE2C will be assessed by quantitative real time PCR on an ABI 7500 Real Time PCR System (Applied Biosystem, Carlsbad, CA). Each reaction (20µL) will consist of 100-500 ng of synthesized cDNA, 500 nM each forward and reverse primer set, and 10 µL of iTaq Universal SYBR Green Supermix ( Bio-Rad, Hercules, CA). The qPCR protocol consists of an initial denaturation at 95C for 2m followed by 40 cycles of 95C for 3s and 60C for 35s, with a final hold at 4C. AR-Responsive gene expression will be normalized to housekeeping gene *RPLPO*. The rationale behind these exploratory analyses derives from existing data demonstrating that alterations of the androgen-regulated TMPRSS2 and ETS transcription factor genes in prostate cancer tissue leads to worse outcome. Similarly, FKBP5, EZH2, H3K27, and UBE2C are considered potential prognostic putative cancer stem cell markers that have been associated with tumor aggressiveness and might be altered by the use of Apalutamide and leuprolide therapy

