	
androsterone and 5<math>\alpha</math>-androstenediol) concentration in benign prostate tissue after neo-adjuvant leuprolide and Apalutamide based on genotype status
 
2. Other androgens (DHT, T, DHEA, androstenediol, 5<math>\alpha</math>-dione, AD, androsterone and 5<math>\alpha</math>-androstenediol) concentration in malignant prostate tissue after neo-adjuvant leuprolide and Apalutamide based on genotype status.
 
3. PSA, FKBP5, TMPRSS2, EZH2, H3K27, and UBE2C expression (via IHC and qPCR) in benign and malignant prostate tissue after neoadjuvant leuprolide and Apalutamide based on genotype status.

Sample Size	
Based on the known frequency of the genotypes in question, approximately 120 male patients will be genotyped prior to enrollment on study. The sample size required to carry-out the objectives of the study will be 57 male patients. Due to logistical restrictions, an accrual goal of 80 male patients may be needed in order to capture all objectives to support this sample size. There won't be any ethnic restrictions for study entry including during the initial genotype identification state.

Disease sites/Conditions	Prostate cancer
Interventions	Leuprolide acetate, Intramuscular injection - 7.5 mg, one time dose on day (-28) $\pm$ 3
	Apalutamide, PO, 240 mg daily, starting day (-28) $\pm$ 3 up to and including the day before radical prostatectomy. Apalutamide will be initiated the same day patients receive their leuprolide acetate injection.

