### 2.2 Secondary Objectives

2.2.1 To evaluate the differential effect of neoadjuvant leuprolide and Apalutamide on other androgen (testosterone (T), dehydroepiandrosterone (DHEA), androstenediol, 5 $\alpha$ -androstenedione (5 $\alpha$ -dione), androstenedione (AD), androsterone and 5 $\alpha$ -androstenediol) concentrations in benign and malignant prostate tissue based on *HSD3B1* genotype.

2.2.2 To compare the level of DHT, T, DHEA, androstenediol, 5 $\alpha$ -dione, AD, androsterone and 5 $\alpha$ -androstenediol between normal and malignant prostate tissue after neoadjuvant treatment with leuprolide and Apalutamide

2.2.3 To determine the safety of the combination of Leuprolide and Apalutamide administered prior to radical prostatectomy

[figure not shown]
2.2.4 To evaluate PSA, FKBP5, TMPRSS2, EZH2, H3K27 and UBE2C tissue expression (via IHC and qPCR) in benign and malignant prostate tissue after treatment with Leuprolide and Apalutamide and Apalutamide.

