### 3 Study design

#### 3.1 Summary

The primary goal of the study is to evaluate the differential effect of neo-adjuvant Apalutamide and leuprolide on dihydrotestosterone (DHT) concentration in benign prostate tissue based on *HSD3B1* genotype. Newly diagnosed, biopsy-proven, intermediate or high-risk prostate cancer patients (G 4+3 or higher,  $\geq$ T2b, PSA  $\geq$  10), who are candidates for radical prostatectomy (RP) are eligible to participate in this study. In order to have enough tumor tissue to perform all of the tests, a minimum tissue requirement of  $\geq$ 1 positive core biopsy. All participating patients will receive a single dose of leuprolide 7.5 mg IM in addition to Apalutamide 240 mg orally daily for four weeks prior to RP. Treatment will be started on day  $(-28) \pm 3$  from the scheduled RP date to minimize the variability of treatment duration. Apalutamide will be continued up to and including the day before radical prostatectomy. Although pre-treatment MRIs of the prostate will be ideal, this protocol does not mandate these imaging studies for study enrollment. Of note, the vast majority of patients undergoing RP at our institutions undergo MRI of prostate for further staging purposes. Thus, the vast majority of our patients will have this completed. Blood will be drawn at baseline and on the day of surgery to evaluate serum PSA and androgen metabolite levels. After RP, fresh tissue from the surgical specimen will be sampled by the GU pathologist (multiple punch biopsies to increase the chance of capturing benign and tumor tissue) with the same methodology that we have previously described. All steroids will be extracted from prostate tissue (20 mg), derivatized by the Girard-T oxime methodology to increase sensitivity, and quantitated by mass spectrometry, as previously described. Expression of PSA transcript and protein will be assessed as we have performed routinely and described previously. Levels of DHT, T, DHEA, androstenediol, 5 $\alpha$ -dione, AD, androsterone, and 5 $\alpha$ -androstane-3 $\beta$ -diol will be measured in all specimens. The underlying hypothesis is that under a recessive model, homozygous *HSD3B1* (1245C) is stabilizing and leads to a gain of function in 3 $\beta$ HSD1 that ultimately results in sustained androgen synthesis compared to wild-type *HSD3B1* (1245A), after treatment with leuprolide. We expect to have intermediate levels of these metabolites in the heterozygous *HSD3B1* (1245C) group.

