## **12 Measurement of Effect**

- 12.1 Benign and malignant tissue concentration of DHT and other androgen (testosterone (T), dehydroepiandrosterone (DHEA), androstenediol, 5 $\alpha$ -androstenedione (5 $\alpha$ -dione), androstenedione (AD), androsterone and 5 $\alpha$ -androstenediol), Direct renin and Aldosterone/Direct Renin Ratio will be measured by IHC as stated in section 10 of the protocol.
- 12.2 PSA, FKBP5, TMPRSS2, EZH2, H3K27, and UBE2C expression in benign and malignant prostate tissue after neoadjuvant leuprolide and Apalutamide will be also analyzed by IHC and qPCR as noted in section 10 of the protocol.
- 12.3 Toxicity will be evaluated using standard CTC guidelines as per section 9 of the protocol. All patients enrolled on study will be evaluable for toxicity from the time of their first treatment with leuprolide and Apalutamide. Surgical safety data will be captured following standardized surgical templates routinely used in the GU clinic.
- 12.4 Although clinical endpoints are not the aim of this biologic study, results of the surgical pathology and PSA changes pre-treatment, during treatment and after surgery will be collected.

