### 14.2 Data Analysis

Hormone concentrations and tissue PSA, TMPRSS2, FKBP5, EZH2, H3K27, and UBE2C measured by qPCR will be summarized as means and standard errors, possibly after data transformation. Differences between genotypes within and between tissue types will be analyzed using linear or non-linear models.

Pearson or Spearman rank correlations will be used to assess associations between the concentrations of the different hormones and molecular markers. All tests of statistical significance will be two-sided.

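### H3K27 is assigned to an RNA-based assay that cannot read a histone residue, and the IHC promised for five of the six tissue markers is not described

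*Combined protocol and SAP*

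**What the plan says.** Three places promise both methods for all six markers. Endpoint 3 of the Protocol Summary lists "PSA, FKBP5, TMPRSS2, EZH2, H3K27, and UBE2C expression (via IHC and qPCR) in benign and malignant prostate tissue". Objective 2.2.4 reads "To evaluate PSA, FKBP5, TMPRSS2, EZH2, H3K27 and UBE2C tissue expression (via IHC and qPCR) in benign and malignant prostate tissue". Section 12.2 says the markers "will be also analyzed by IHC and qPCR as noted in section 10 of the protocol", so it leaves the methods to section 10.

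Section 10 does not match that promise. Section 10.3 is a single sentence that begins "IHC for PSA will be performed as routinely done by" and refers to routine practice in the pathology department. It names no other marker, and its heading speaks of prostate tumor tissue only. Section 10.5 covers mRNA: "Expression for PSA, TMPRSS2, FKBP5, EZH2, H3K27, and UBE2C will be assessed by quantitative real time PCR". The template is stated: "Extracted RNA will be synthesized into cDNA using an iScript cDNA Synthesis Kit". The same section calls these analyses exploratory.

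The design summary in 3.1 names a protein readout for PSA alone: "Expression of PSA transcript and protein will be assessed as we have performed routinely".

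In 14.2 the list of markers to be summarised ends "H3K27, and UBE2C measured by qPCR will be summarized as means and standard errors". The sentences that follow, on models by genotype and tissue type and on correlations between hormones and molecular markers, name no assay.

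**The concern.** H3K27 is standard notation for lysine 27 of histone H3. What is of biological interest is the modification at that site, such as methylation or acetylation. The site is part of a protein and is not a gene, so primers on cDNA have nothing of that name to amplify. Amplifying a histone H3 transcript would say nothing about the modification. IHC could read it, but section 10 describes no IHC for it. The protocol does not say which modification is meant, names no surrogate gene, and omits H3K27 from its abbreviation list.

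Three things are at stake:

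- **H3K27.** Carried out as 10.5 and 14.2 are written, this marker yields either no result or one that cannot be interpreted. Methylation and acetylation are different readouts, and leaving the choice open allows it to be made after data are seen.
- **FKBP5, TMPRSS2, EZH2 and UBE2C.** The endpoint promises protein as well as mRNA, but only the mRNA method is described.
- **PSA protein.** The Protocol Summary and 1.7 hypothesise that PSA expression will be similar across genotypes despite higher DHT. PSA staining bears directly on this, yet no score is defined for it.

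**Working it through.** No sample size, power or error-rate figure enters this point, so the check sets the promises beside the methods and the analysis text. The only input from outside the documents is the standard meaning of the label H3K27.

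| Marker | Promised (Protocol Summary, 2.2.4, 12.2) | qPCR in 10.5 | IHC in 10.3 | Named in 14.2 |
|---|---|---|---|---|
| PSA | IHC + qPCR | yes | yes (heading: tumor) | qPCR |
| FKBP5 | IHC + qPCR | yes | none | qPCR |
| TMPRSS2 | IHC + qPCR | yes | none | qPCR |
| EZH2 | IHC + qPCR | yes | none | qPCR |
| UBE2C | IHC + qPCR | yes | none | qPCR |
| H3K27 | IHC + qPCR | listed, but cannot be read from cDNA | none | qPCR |

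**Promised per tissue:** 6 markers × 2 methods = 12 readouts. One of these, H3K27 by qPCR, cannot be delivered at all, so 12 − 1 = 11 are achievable.

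**Described with a usable method, tumor tissue:** 5 by qPCR (six listed less H3K27) + 1 by IHC (PSA) = 6.

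**Described with a usable method, benign tissue:** 5 by qPCR + 0 by IHC = 5 if the 10.3 heading is read literally. If the heading is loose wording and PSA is stained in both tissues, the count is again 6.

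**Promised by IHC without a described method:** 6 − 1 = 5 markers in tumor. Leaving out H3K27, 5 − 1 = 4 markers (FKBP5, TMPRSS2, EZH2, UBE2C) keep a usable mRNA readout and lack a described protein one.

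**H3K27:** one assay described (qPCR), none of them valid, so 0 of 2.

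**Analysis.** Section 14.2 names six marker variables, all by qPCR. Five are usable and one (H3K27) is not. It names no IHC variable.

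**The case against.** The strongest reply is that the measurements are planned and only the description is thin. The Protocol Summary, 2.2.4 and 12.2 all assign IHC to H3K27 and to the other markers. Section 10.3 gives no antibody or scoring even for PSA, so its silence on the rest may be brief drafting rather than a decision not to stain. This stands in part. A reader might infer that H3K27 will not be validly measured, or that four markers have lost their protein readout; the documents support only the statement that no such method is described. Nor does the promise cure the gap: 12.2 points back to section 10, and 3.1 also names PSA alone for protein.

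A reader might also infer that PSA staining has no place in the analysis. That goes too far. Only the summary-statistics sentence in 14.2 is tied to qPCR; its modelling and correlation sentences do not exclude IHC data. What is missing is a named variable and a score.

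It can also be said that the harm is speculative. Section 10.5 gives no primer sequences for any marker, so the laboratory would have to choose a target for H3K27 and would probably notice the problem then. That is fair: the documents do not show that an uninterpretable value would actually be tested. It does not justify leaving a method in the plan that cannot work.

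Finally, the markers carry little weight. Section 10.5 calls them exploratory. The Protocol Summary and 2.2.4 nevertheless list them as secondary, and 14.1 extends its power statement to molecular markers.

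**Conclusion.** The point holds. Assigning H3K27 to qPCR in 10.5 and 14.2 is wrong as written and is not merely short on detail. Section 10.3 does not deliver what the Protocol Summary, 2.2.4 and 12.2 promise: five of the six markers have no IHC method described. H3K27 has no valid measurement described at all. In all, 6 of 12 promised readouts have a usable described method in tumor, and 5 or 6 of 12 in benign tissue depending on how the 10.3 heading is read.

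The consequence is limited. A reader might infer that the trial's main result is at risk; it is not. The primary endpoint is DHT in benign tissue, which uses none of these markers, and the sample size of 57 does not depend on them. The correction is worth making because it is cheap, but the trial does not turn on it.

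The conclusion assumes that H3K27 carries its usual meaning and does not stand for some unnamed transcript, and that section 10 is where the marker methods are set. Section 12.2 says the latter, and 10.3 and 10.5 cite no separate laboratory manual.

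**What to change.** 1. Delete H3K27 from the qPCR lists in 10.5 and 14.2.
2. Then choose one course for H3K27. Either name the modification and make it an IHC readout, with the stain and its score given in 10.3 and 14.2, or drop H3K27 from the objectives, the endpoints and 12.2.
3. For FKBP5, TMPRSS2, EZH2 and UBE2C, reconcile 10.3 with the Protocol Summary, 2.2.4 and 12.2. Describing the promised IHC and stating that these four are mRNA-only are both acceptable, provided every section says the same.
4. State in 14.2 that PSA IHC is analysed by genotype in benign and malignant tissue with one pre-defined score, and align the 10.3 heading with both tissues.

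Most of the cost is wording. Any stain that is kept has already been promised, but the work is real: up to five stains beyond PSA (H3K27 and the other four), and section 10 allots tissue to steroids (20 mg) and RNA (under 20 mg) without allotting any to IHC. The downside of the cheaper route is that some markers become formally mRNA-only or are dropped.
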